### Table 14.2.4.13 Treatment Comparison of Change from Baseline in PANSS Total Score at Week 6 by Age of Onset Full Analysis Set

This table will be similar to 14.2.4.1. 'Female' and 'Male' are replaced with 'Onset Age < 25' and 'Onset Age >= 25'.

### Table 14.2.4.14 Treatment Comparison of Change from Baseline in CGI-S Total Score at Week 6 by Age of Onset

#### Full Analysis Set

This table will be similar to 14.2.4.1. 'Female' and 'Male' are replaced with 'Onset Age < 25' and 'Onset Age >= 25'. Footnotes will be:

Note: CGI-S = Clinical Global Impression - Severity of Illness Scale, LSM = Least Squares Mean, SE = Standard Error, CI = Confidence Interval, N = number of subjects in the full analysis set by treatment group.

Note: Baseline is defined as the last non-missing measurement taken prior to first dose of double-blind study medication. Note: Percentages are calculated as (n/N) \* 100.

Note: CGI-S score is determined by answering the question "Considering your total clinical experience with this particular population, how mentally ill is the subject at this time?" on a scale of 0-7, with 0 indicating not assessed and 7 indicating the most extremely ill subjects.

Note: The mixed linear repeated measures model includes treatment, country, visit, treatment by visit interaction, and baseline value as covariates, and subject as random effect. The correlation of repeated measures within a subject is estimated with an unstructured covariance matrix. The Kenward-Rogers method is used to estimate the denominator degrees of freedom.

Note: To perform this assessment, the rater or Investigator answers the following question: "Considering your total clinical experience with this particular population, how mentally ill is the subject at this time?" Higher values represent greater severity of illness. The maximum score is 7.

### Table 14.2.4.15 Treatment Comparison of Change from Baseline in PANSS Total Score at Week 6 by Disease Duration Full Analysis Set

This table will be similar to 14.2.4.1. Instead of 2 categories of 'Female' and 'Male', there will be 4 categories of '< 5 years', '>= 5 to < 10 years', '>= 10 to < 20 years', and '>= 20 years'.

Author:	[name]	Version Number:	Draft 2
		Version Date:	09Jan2017
			Page 72 of 144

### Table 14.2.4.16 Treatment Comparison of Change from Baseline in CGI-S Score at Week 6 by Disease Duration Full Analysis Set

This table will be similar to 14.2.4.1.

Instead of 2 categories of 'Female' and 'Male', there will be 4 categories of '< 5 years', '>= 5 to < 10 years', '>= 10 to < 20 years', and '>= 20 years'.

Footnotes will be:

Note: CGI-S = Clinical Global Impression - Severity of Illness Scale, LSM = Least Squares Mean, SE = Standard Error, CI = Confidence Interval, N = number of subjects in the full analysis set by treatment group.

Note: Baseline is defined as the last non-missing measurement taken prior to first dose of double-blind study medication.

Note: CGI-S score is determined by answering the question "Considering your total clinical experience with this particular population, how mentally ill is the subject at this time?" on a scale of 0-7, with 0 indicating not assessed and 7 indicating the most extremely ill subjects.

Note: Percentages are calculated as (n/N) \* 100.

Note: The mixed linear repeated measures model includes treatment, country, visit, treatment by visit interaction, and baseline value as covariates, and subject as random effect. The correlation of repeated measures within a subject is estimated with an unstructured covariance matrix. The Kenward-Rogers method is used to estimate the denominator degrees of freedom.

Author: A

[name]

Version Number:

Version Date:

Draft 2 09Jan2017 Page **73** of **144**  Noven Pharmaceuticals Version No. 1.0 Protocol No. HP-3070-GL-04 14 September 2018

Noven Pharmaceuticals, Inc. STATISTICAL ANALYSIS PLAN: PROTOCOL HP-3070-GL-04

1.3 Safety

Author:

[name]

Version Number: Version Date: Draft 2 09Jan2017 Page 74 of 144

Noven Pharmaceuticals, Inc. Protocol HP-3070-GL-04 Page 1 of x

#### Table 14.3.1.1 Overview of Adverse Events Safety Analysis Set

		HP-3070 18.0 mg		HP-3070 9.0 mg		Placebo	
		(N=x:	xx)	(N=XXX)		(N=xxx)	
	Statistic	Subjects [a]	Events [b]	Subjects [a]	Events [b]	Subjects [a]	Events [b]
Any AE	n (%)	xx (xx.x)	XX	xx (xx.x)	XX	xx (xx.x)	XX
Any TEAE	n (%)	xx (xx.x)	XX	xx (xx.x)	XX	xx (xx.x)	XX
Any Severe TEAE	n (%)	xx (xx.x)	XX	xx (xx.x)	xx	xx (xx.x)	XX
Any Related TEAE	n (%)	xx (xx.x)	XX	xx (xx.x)	XX	xx (xx.x)	XX
Any TEAE Leading to Discontinuation	n (%)	xx (xx.x)	XX	xx (xx.x)	XX	xx (xx.x)	XX
of Study Medication							
Any Serious TEAE	n (%)	xx (xx.x)	XX	xx (xx.x)	XX	xx (xx.x)	XX
Any Related Serious TEAE	n (%)	xx (xx.x)	XX	xx (xx.x)	XX	xx (xx.x)	XX
Any TEAE Leading to Death	n (%)	xx (xx.x)	XX	xx (xx.x)	XX	xx (xx.x)	XX
Any TEAE Occurring at Patch	n (%)	xx (xx.x)	XX	xx (xx.x)	XX	xx (xx.x)	XX
Application Site							

Note: AE = Adverse Event, TEAE = Treatment-Emergent Adverse Event, N = number of subjects in the safety analysis set by treatment group.

Note: TEAEs are defined as all AEs which start (or increase in severity) prior to, on or after the date of first dose of double-blind study medication through the 30 day follow-up period.

Note: Related is defined as any investigator assessment of possible or probable. TEAEs with missing relationship to study medication are counted as related.

Note: Percentages are calculated as (n/N)\*100.

[a]: Subjects with multiple events in the same category are counted only once in that category. Subjects with events in more than one category are counted once in each of those categories.

[b]: Multiple events for a subject that are in the same AE category are counted multiple times in that AE category. Multiple events belonging to more than one AE category are counted multiple times in each of those AE categories.

Noven/HP-3070/XWA17541/Biostatistics/Production/Tables/xxxxx.sas ddmmmyyyy hh:mm

Author:

[name]

Version Number: Version Date: 0

Draft 2 09Jan2017 Page 75 of 144

IMS Health & Quintiles are now

Noven Pharmaceuticals, Inc. Protocol HP-3070-GL-04 Page 1 of x

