# **16.1. TREATMENT EMERGENT ADVERSE EVENTS**

Adverse events will be coded using MedDRA central coding dictionary, version 20.1 . Severity for AEs is classified in the eCRF as 'mild', 'moderate', or 'severe'.

Treatment Emergent Adverse Events (TEAEs) are defined as AEs that first occurred or worsened in severity after the first administration of the study drug.

TEAEs during the double-blind treatment period is defined as an AE with a start date on or after the date of first dose of double-blind study medication through the 30 day follow-up period. The same rule applies for Run-in Period (for those enrolled in the double-blind period)

SAEs that occur within 30 days after last dose of double-blind study medication will be reported.

In the case where it is not possible to define an AE as treatment-emergent or not, the AE will be classified by the worst case i.e. treatment-emergent.

Adverse event summaries will include numbers of events and subject incidence (number and percentage of subjects with at least one event) by treatment group and further categorization as described below.

An overview of AEs within each of the categories described below will be provided:

- AEs (for those who enrolled in the double-blind period) which occurred during the single-blind run-in or double-blind period
- TEAEs
- TEAEs by highest severity
- TEAEs by strongest relationship to study medication (Not Related, Related)
- TEAEs leading to study medication discontinuation
- Serious TEAEs
- Serious TEAEs by strongest relationship to study medication (Not Related, Related)
- TEAEs leading to death
- Commonly occurring TEAEs (defined as those which occur in 5% or more of the subjects in any treatment arm)
- TEAEs at the patch application site

Document:	\\quintiles.net\Enterprise\Apps\sasdata\SASb\SAS\Noven\HP-		
	3070\XWA17541\Biostatistics\Documentation\SAP\Final 6\Noven HP-3070-GL-04 SAP text Final		
	6_18Jan2018.docx		
Author:	[name]	Version Number:	Final 6
		Version Date:	18Jan2018
Template No:	CS_TP_BS016 - Revision 3	Reference: (	S WL BS005

Effective Date: 01May2012

Copyright © 2012 Quintiles Transnational Corp. All rights reserved.

Noven Pharmaceuticals, Inc. STATISTICAL ANALYSIS PLAN: PROTOCOL HP-3070-GL-04 Page 34 of 50

Multiple occurrences of the same category of AEs will be counted once for each subject, at the highest severity and strongest relationship to study medication as appropriate.

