## Table 14.3.1.14 Treatment-Emergent Adverse Events at Patch Application Site During the Double-Blind Period by Preferred Term and Severity Safety Analysis Set

	HP-3070 18.0 mg	HP-3070 9.0 mg	Placebo
Preferred Term	(N=XXX)	(N=XXX)	(N=xxx)
Severity	n (%)	n (%)	n (%)
Total number of Dermal TEAEs	XX	XX	XX
Subjects with any Dermal TEAE	xx (xx.x)	xx (xx.x)	xx (xx.x)
Preferred Term 1	xx (xx.x)	xx (xx.x)	xx (xx.x)
Mild	xx (xx.x)	xx (xx.x)	xx (xx.x)
Moderate	xx (xx.x)	xx (xx.x)	xx (xx.x)
Severe	xx (xx.x)	xx (xx.x)	xx (xx.x)
Preferred Term 2	xx (xx.x)	xx (xx.x)	xx (xx.x)
Mild	xx (xx.x)	xx (xx.x)	xx (xx.x)
Moderate	xx (xx.x)	xx (xx.x)	xx (xx.x)
Severe	xx (xx.x)	xx (xx.x)	xx (xx.x)
Preferred Term 3	xx (xx.x)	xx (xx.x)	xx (xx.x)
Mild	xx (xx.x)	xx (xx.x)	xx (xx.x)
Moderate	xx (xx.x)	xx (xx.x)	xx (xx.x)
Severe	xx (xx.x)	xx (xx.x)	xx (xx.x)

Note: TEAE = Treatment-Emergent Adverse Event, AE = Adverse Event, N = number of subjects in the safety analysis set by treatment group.

Note: TEAEs are defined as all AEs which start (or increase in severity) prior to, on or after the date of first dose of doubleblind study medication through the 30 day follow-up period.

Note: TEAEs with a missing severity are counted as severe.

Note: Percentages are calculated as (n/N)\*100.

Note: Subjects with multiple events in the same category are counted only once in that category. Subjects with events in more than one category are counted once in each of those categories.

Note: This summary is sorted by decreasing frequency of preferred term in the HP-3070 18.0mg column.

Note: Adverse events are coded using Medical Dictionary for Regulatory Activities (MedDRA) Version xx.x.

Noven\HP-3070\XWA17541\Biostatistics\Production\Tables\xxxxx.sas ddmmmyyyy hh:mm

 Author:
 [name]
 Version Number:

 Version Date:
 Version Date:

134

Noven Pharmaceuticals Version No. 1.0

Protocol No. HP-3070-GL-04 14 September 2018

Noven Pharmaceuticals, Inc. STATISTICAL ANALYSIS PLAN: PROTOCOL HP-3070-GL-04

IMS Health & Quintiles are now

Noven Pharmaceuticals, Inc. Protocol HP-3070-GL-04

Page 1 of x

Laboratory Test (SI Unit)	Visit	Statistic	HP-3070 18.0 mg (N=xxx)	HP-3070 9.0 mg (N=xxx)	Placebo (N=xxx)
Hemoglobin (g/dL)					
	Baseline	n	XX	XX	XX
		Mean	XX.X	xx.x	XX.X
		SD	xx.xx	xx.xx	XX.XX
		Median	XX	XX	xx
		Min	XX	XX	XX
		Max	XX	XX	xx
	Week 3	n	XX	XX	XX
		Mean	XX.X	XX.X	XX.X
		SD	xx.xx	xx.xx	xx.xx
		Median	XX	XX	xx
		Min	XX	XX	XX
		Max	XX	XX	XX
	Change from Baseline to Week 3	n	XX	XX	xx

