## Listing 16.2.3.1.1 Adverse Events Safety Analysis Set

Treatment Group: HP-3070 18.0 mg

	-								
Subject ID		AE	System Organ Class/ Preferred Term/	Start Date (Study Day)/ Stop Date				Occur at Patch	
Subject iD	Period	Number	Verbatim Term	(Study Day)	TEAE	SAE	AESI	Application Site	Severity
xxxx-xxxx	SB	XX	xxxxxxxxxx/	YYYY-MM-DD (xx)/	Ν	Ν	N	Ν	Mild
			xxxxxxxx/	YYYY-MM-DD (xx)					
			*****						
	DB	XX	**********	YYYY-MM-DD (xx)/	Y	Y	N	Y	Moderate
			xxxxxxxxx/	YYYY-MM-DD (xx)					
			*****						

Note: SB = Single-Blind, DB = Double-Blind, FU = Follow-up, TEAE = Treatment-Emergent Adverse Event, SAE = Serious Adverse Event, AE = Adverse Event, AESI = Adverse Event of Special Interest.

Note: TEAEs are defined as all AEs which start (or increase in severity) on or after the date of first dose of double-blind study medication through the 30 day follow-up period.

Note: Potential Hy's Law events are to be entered as AESIs.

Note: During the SB period, study day is calculated relative to the first dose of study medication during the run-in period. During the DB and FU periods, study day is calculated relative to the first dose of double-blind study medication.

Note: Adverse events are coded using Medical Dictionary for Regulatory Activities (MedDRA) Version xx.x.

Noven\HP-3070\XWA17541\Biostatistics\Production\Listings\xxxxx.sas ddmmmyyyy hh:mm Programming note: Repeat for HP-3070 9.0 mg, and Placebo.

Author: [name]

Version Number:

Version Date:

Draft 2 09Jan2017 Page **130** of **144** 

Noven Pharmaceuticals, Inc. Protocol HP-3070-GL-04 Page 2 of x

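### The treatment-emergent footnotes in the adverse event table shells set no lower time limit, contradicting SAP section 16.1 and the adverse event listings

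*SAP*

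**What the plan says.** The SAP defines a treatment-emergent adverse event (TEAE) in three places.

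- **Section 16.1, text.** A general sentence covers "AEs that first occurred or worsened in severity after the first administration of the study drug". The next sentence sets the double-blind rule as "an AE with a start date on or after the date of first dose of double-blind study medication through the 30 day follow-up period". It is followed by "The same rule applies for Run-in Period (for those enrolled in the double-blind period". The overview list then has an adverse event category for enrolled subjects covering events "which occurred during the single-blind run-in or double-blind period", separate from the TEAE category.
- **Table shells.** The footnote of Table 14.3.1.1 says "TEAEs are defined as all AEs which start (or increase in severity) prior to, on or after the date of first dose" of double-blind medication, through the 30-day follow-up. Tables 14.3.1.2, 14.3.1.3, 14.3.1.5 and 14.3.1.14 carry the same "prior to, on or after the date of first dose". Tables 14.3.1.4 and 14.3.1.6 to 14.3.1.13 are specified as similar to one of these.
- **Listing shells.** Listing 16.2.3.1.1 says "TEAEs are defined as all AEs which start (or increase in severity) on or after the date of first dose of double-blind" medication, and Listing 16.2.3.1.2 uses the same rule. The sample single-blind event in Listing 16.2.3.1.1 is flagged as not treatment-emergent.

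Section 3.1 gives every subject a placebo patch for at least 3 days before randomisation, in a run-in of 3 to 14 days.

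**The concern.** A window that opens before, on or after a date has no opening limit. Under the table footnote, an event that began on the run-in placebo patch counts as treatment-emergent, although the subject had not yet received randomised treatment. Onset would then no longer separate the Any AE and Any TEAE rows of Table 14.3.1.1. The remaining TEAE tables are titled for the double-blind period and would contain events from outside it.

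Two consequences would follow. The tables and listings would classify the same event differently. The displayed TEAE incidence would also include a background common to all arms, which raises every percentage and pulls the contrast between HP-3070 and placebo toward the null. Because section 16 plans no tests on safety data unless otherwise specified, these displayed percentages are themselves the safety result.

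**Working it through.** **Step 1: the wording side by side.**

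| Place | Start of window | Worsening included |
|---|---|---|
| 16.1, general sentence | after first study drug, not said which | yes |
| 16.1, double-blind sentence | on or after first double-blind dose | not stated |
| Table footnotes | before, on or after first double-blind dose | yes |
| Listing footnotes | on or after first double-blind dose | yes |

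Only the table footnotes drop the lower limit. The general sentence in 16.1 does not settle the matter alone, because section 6.1 also speaks of a first dose of study medication during the run-in.

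**Step 2: is the wide wording deliberate?** The concomitant medication footnote of Table 14.1.10 uses nearly the same phrase, but adds that the medication ended on or after the first dose or was ongoing. That second condition makes the phrase meaningful there. The adverse event footnote has none. This is consistent with carried-over wording but does not prove it.

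**Step 3: effect if the footnote is programmed.** The SAP states no figure to reproduce. Let p be the double-blind subject incidence in an arm and r the run-in incidence of the same event, equal across arms because the run-in precedes randomised treatment. Assume run-in and double-blind events are independent.

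- Displayed incidence = 1 − (1−r)(1−p)
- Displayed risk difference = (1−r) × (p_active − p_placebo)

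For example, with r = 5%: 1 − 0.95 × 0.95 = 9.75% and 1 − 0.95 × 0.90 = 14.5%.

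All rates below are assumed; the SAP gives none.

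| r | 5% vs 10% becomes | Difference (points) | Ratio | 40% vs 50% becomes | Difference (points) | Ratio |
|---|---|---|---|---|---|---|
| 0 | 5.0 vs 10.0 | 5.0 | 2.00 | 40.0 vs 50.0 | 10.0 | 1.25 |
| 2% | 6.9 vs 11.8 | 4.9 | 1.71 | 41.2 vs 51.0 | 9.8 | 1.24 |
| 5% | 9.75 vs 14.5 | 4.75 | 1.49 | 43.0 vs 52.5 | 9.5 | 1.22 |
| 10% | 14.5 vs 19.0 | 4.5 | 1.31 | 46.0 vs 55.0 | 9.0 | 1.20 |
| 20% | 24.0 vs 28.0 | 4.0 | 1.17 | 52.0 vs 60.0 | 8.0 | 1.15 |

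The r = 0 row is what the corrected footnote would display. The difference shrinks only by the factor (1−r); the ratio moves more, above all for uncommon events.

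**Step 4: the common-event threshold.** An event with 3% in the double-blind period and 3% in the run-in shows as 1 − 0.97 × 0.97 = 5.9%, which crosses the 5% limit of section 16.1.5. With 2% in the run-in it shows as 1 − 0.97 × 0.98 = 4.9% and does not.

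**Step 5: what does not move.** Run-in events add the same expected number of events per subject to each arm, so expected between-arm differences in event counts are unchanged.

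**The case against.** The strongest reply is that this is one side of an internal contradiction, and most of the SAP is on the other side. The double-blind sentence in 16.1, the listings, the table titles and the separate Any AE row all point to the narrower window. The body text is Final 6, while the shell pages are marked Draft 2. Section 16.1.6 separately limits the patch-site summary to the double-blind period. This stands: run-in events are counted only if the footnote is followed over the text. It does not make the footnote harmless, because section 8 says the templates describe the format and content of the tables.

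A reader might infer that every drug-placebo safety contrast is diluted. The SAP does not support that. Laboratory, ECG, vital-sign, movement-scale, C-SSRS, adhesion and irritation-scale summaries do not use the TEAE definition. Subjects who died or withdrew before a double-blind patch are outside the Safety Analysis Set (section 5.4), so the death and discontinuation rows would barely change.

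A reader might also apply one sizeable shrinkage, say 10 to 25%, to all the tables. That would need an any-event run-in rate that the SAP does not give, and it would concern the Any TEAE row only. For a single preferred term, r is the run-in rate of that term, which cannot exceed the any-event rate and would usually be far smaller.

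On worsening, the gap in 16.1 is modest. The general sentence and both footnote versions include it, and the double-blind sentence may only be assigning events to a period.

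**Conclusion.** The table footnotes are wrong as written and should be fixed. They contradict section 16.1, the listings and the titles of the double-blind TEAE tables. If programmed literally, they would overstate TEAE subject incidence, multiply TEAE risk differences by (1−r), and make tables and listings disagree on which events are treatment-emergent.

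The size cannot be fixed from the SAP. Over the assumed range of r from 2% to 20%, the risk difference loses 2% to 20% of its value. The factor assumes equal run-in rates across arms and independence between periods. Without independence, the displayed difference is (1−r) times the difference among subjects with no run-in event, so the loss could be smaller or larger.

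It would go too far to say that the plan has settled on counting run-in events. The point is an unresolved contradiction in the definition behind the main adverse event tables. No hypothesis test and no efficacy result depends on it.

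**What to change.** 1. Delete *prior to,* from the footnotes of Tables 14.3.1.1, 14.3.1.2, 14.3.1.3, 14.3.1.5 and 14.3.1.14, and so from the tables modelled on them, to match Listing 16.2.3.1.1.
2. In section 16.1, add worsening in severity to the double-blind TEAE sentence.
3. In the general sentence of 16.1, state whether study drug means the run-in placebo patch or the double-blind patch.
4. Report run-in events separately, either in the Any AE row of Table 14.3.1.1 or in a distinct run-in TEAE row. The choice must agree with the sentence that applies the same rule to the run-in.

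The cost is footnote and definition wording plus one derivation flag. No new data are needed. It should be settled before the TEAE tables are programmed and the treatment codes are opened.

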#### Table 14.3.1.2 Treatment-Emergent Adverse Events During the Double-Blind Period by System Organ Class and Preferred Term Safety Analysis Set

	HP-3070 18.0 mg	HP-3070 9.0 mg	Placebo
System Organ Class	(N=xxx)	(N=XXX)	(N=XXX)
Preferred Term	n (%)	n (%)	n (%)
Total number of TEAE	XX	XX	XX
Subjects with any TEAE	xx (xx.x)	xx (xx.x)	xx (xx.x)
SYSTEM ORGAN CLASS 1	xx (xx.x)	xx (xx.x)	xx (xx.x)
Preferred Term 1	xx (xx.x)	xx (xx.x)	xx (xx.x)
Preferred Term 2	xx (xx.x)	xx (xx.x)	xx (xx.x)
	xx (xx.x)	xx (xx.x)	xx (xx.x)
SYSTEM ORGAN CLASS 2	xx (xx.x)	xx (xx.x)	xx (xx.x)
Preferred Term 1	xx (xx.x)	xx (xx.x)	xx (xx.x)
Preferred Term 2	xx (xx.x)	xx (xx.x)	xx (xx.x)
	xx (xx.x)	xx (xx.x)	xx (xx.x)

Note: TEAE = Treatment-Emergent Adverse Event, AE = Adverse Event, N = number of subjects in the safety analysis set by treatment group.

Note: TEAEs are defined as all AEs which start (or increase in severity) prior to, on or after the date of first dose of doubleblind study medication through the 30 day follow-up period.

Note: Percentages are calculated as (n/N) \* 100.

Note: Subjects with multiple events in the same category are counted only once in that category. Subjects with events in more than one category are counted once in each of those categories.

Note: This summary is sorted by decreasing frequency of system organ class, and within system organ class, by decreasing frequency of preferred term in the HP-3070 18.0mg column.

Note: Adverse events are coded using Medical Dictionary for Regulatory Activities (MedDRA) Version xx.x.

Noven\HP-3070\XWA17541\Biostatistics\Production\Tables\xxxxx.sas ddmmmyyyy hh:mm Programming note: SOC should be displayed in all caps. Preferred Term should include lower case.

Author: [name]

Version Number: Version Date: Draft 2 09Jan2017 Page **76** of **144** 

IMS Health & Quintiles are now

Noven Pharmaceuticals, Inc. Protocol HP-3070-GL-04 Page 1 of x

#### Table 14.3.1.3 Treatment-Emergent Adverse Events During the Double-Blind Period by System Organ Class, Preferred Term, Relationship to Study Medication, and Severity Safety Analysis Set

		HP-3070 18.0 mg		HP-3070 9.0 mg		Placebo	
System Organ Class	Relationship	(N=X)	XX)	(N=X	XX)	(N=X	XXX)
Preferred Term	Severity	Subjects [a]	Events [b]	Subjects [a]	Events [b]	Subjects [a]	Events [b]
Subjects with any TEAE	Related	xx (xx.x)	XX	xx (xx.x)	XX	xx (xx.x)	XX
	Mild	xx (xx.x)	XX	xx (xx.x)	XX	xx (xx.x)	XX
	Moderate	xx (xx.x)	XX	xx (xx.x)	XX	xx (xx.x)	XX
	Severe	xx (xx.x)	XX	xx (xx.x)	XX	xx (xx.x)	XX
	Not Related	xx (xx.x)	XX	xx (xx.x)	XX	xx (xx.x)	XX
	Mild	xx (xx.x)	XX	xx (xx.x)	XX	xx (xx.x)	XX
	Moderate	xx (xx.x)	XX	xx (xx.x)	XX	xx (xx.x)	XX
	Severe	xx (xx.x)	XX	xx (xx.x)	XX	xx (xx.x)	XX
SYSTEM ORGAN CLASS 1	Related	xx (xx.x)	XX	xx (xx.x)	XX	xx (xx.x)	XX
	Mild	xx (xx.x)	xx	xx (xx.x)	XX	xx (xx.x)	XX
	Moderate	xx (xx.x)	XX	xx (xx.x)	XX	xx (xx.x)	XX
	Severe	xx (xx.x)	XX	xx (xx.x)	XX	xx (xx.x)	XX

Note: TEAE = Treatment-Emergent Adverse Event, AE = Adverse Event, N = number of subjects in the safety analysis set by treatment group. Note: TEAEs are defined as all AEs which start (or increase in severity) prior to, on or after the date of first dose of double-blind study medication through the 30 day follow-up period.

Note: Related is defined as any investigator assessment of possible or probable. TEAEs with missing relationship to study medication are counted as related.

Note: TEAEs with a missing severity are counted as severe.

[a]: Subjects with more than one TEAE are counted once in each category. The worst case relationship is summarized, at the maximum severity.

[b]: Multiple events for a subject that are in the same AE category are counted multiple times in that AE category.

Note: Adverse events are coded using Medical Dictionary for Regulatory Activities (MedDRA) Version xx.x.

Note: Percentages are calculated as (n/N)\*100.

Noven\HP-3070\XWA17541\Biostatistics\Production\Tables\xxxxx.sas ddmmmyyyy hh:mm

Programming note: Repeat for all Related and Not Related options for every SOC and PT. SOC should be displayed in all caps. Preferred Term should include lower case.

Author:	[name]	Version Number:	Draft 2
		Version Date:	09Jan2017
			Page 77 of 144

Programming note: In the Subjects [a] column, each subject is counted once per SOC/PT. At a given SOC or PT level, identify the worst case relationship per subject, then within that relationship level identify the worst case severity. In the Events [b] column, all TEAEs meeting the relationship/severity condition should be counted. (A subject may contribute to the events count in a row where he/she is not counted at the subject level, if it is not the worst case event.)

